1.1. Title and trial registration

Assessment of a viral load result-driven automated differentiated service delivery model for participants taking antiretroviral therapy in Lesotho: Viral load triggered ART care in Lesotho (VITAL)

ClinicalTrials.gov, NCT04527874, registered on 27 August 2020

1.2. SAP version

V1.1, dated 28 July 2025

This SAP lays out the planned primary statistical analyses that look at the clinical effectiveness of the VITAL model of care within the VITAL trial.

1.3. Protocol version

V4, dated 23 July 2023

1.4. SAP revisions

Version	Date	Justification for each SAP revision	Timing of SAP revision in relation to study
1.1	28.07.2025	- Change in secondary endpoint 13 due to data issues: updated from "having received a course of TPT throughout the study" to "having ever received a course of TPT," as the first TPT measurement was not consistently collected at enrolment, making the baseline estimate unreliable. - Change in sensitivity analysis 2 due to methodological clarification: updated from "multiple imputation" to "imputation," as a single imputation method was used rather than a multiple imputation approach - Change in secondary endpoint analyses: no longer reporting adjusted risk differences for secondary endpoints due to convergence issues. - Clarification: No regression model will be fitted if the number of events per model parameter is below 10, to avoid overfitting and to ensure reliable coefficient estimation.	During analysis

2.1. Background and rationale

To sustainably provide good quality HIV care to the increasing number of people with HIV receiving antiretroviral therapy (ART), care delivery should shift from a "one-size-fits-all" approach to differentiated care models. Reducing the frequency of clinic visits through multi-months distribution of ART among people with suppressed viral load (VL) and no other clinical problems could save time and transport cost of people with suppressed VL while reducing the workload at health care facilities. This may allow focusing on people with elevated VL and/or other clinical problems and could thereby improve clinical outcomes of people with HIV. The VITAL model of care thus automatically differentiates HIV care based on previous VL results while providing a broad range of preference-based eHealth support to participants and clinical decision support to health care providers.

2.2. Objectives

The **primary objective** is to assess if the proposed automated differentiated service delivery model (aDSDM) is at least non-inferior in the proportion of participants engaged in care and virally suppressed <50 copies/mL at 24 months (window: 16-28 months) follow-up (intention-to-treat (ITT) population)

The secondary objectives are:

- To test if the proposed automated differentiated service delivery model (aDSDM) is superior in the proportion of participants engaged in care and virally suppressed <50 copies/mL at 24 months (window: 16-28 months) follow-up (intention-to-treat (ITT) population); and
- To test if the proposed aDSDM is cost-effective if the intervention is found to be superior or cost-saving if the intervention is found to be non-inferior.

3. Study methods

3.1. Trial design

Full details of the trial are available in the published protocol (2).

VITAL is a multicenter, pragmatic, cluster-randomized, open-label, non-inferiority trial. The rationale for a cluster randomized design with clinics as clusters is to minimize the risk of cross-contamination between the study arms. Also, the pragmatic cluster-randomized design is the method of choice for the evaluation of the effect of a model of care on patient outcomes. The study is conducted at 18 clinics in two districts of Lesotho (Butha-Buthe, Mokhotlong).

3.2. Randomization

Randomization is done at cluster (clinics) level with a 1:1 allocation and stratified by district (Butha-Buthe vs Mokhotlong). To obtain consent and to maximize transparency and ownership from the clinics, randomization events involving representatives of all health facilities and the District Health Management Team were conducted in each district. For randomization, opaque, equally-sized and sealed envelopes containing the group allocation (control or intervention) were held in a typical Lesotho hat (Mokorotlo). An independent person randomized the allocation sequence by drawing from another typical Lesotho hat (Mokorotlo) an equally-sized and sealed envelopes containing the names of health facility representatives one after each other. According to this sequence health center representatives drew their arm allocation, which was disclosed only after all participants had drawn an envelope at very end of drawing event.

clinic	stratifictation factor district	allocation
Makhunoane	Butha-Buthe	control
Linakeng	Butha-Buthe	intervention
Tsime	Butha-Buthe	control
St. Peters	Butha-Buthe	control
St. Paul	Butha-Buthe	control
Boiketsiso	Butha-Buthe	intervention
Motete	Butha-Buthe	intervention
Rampai	Butha-Buthe	control
Ngoajane	Butha-Buthe	intervention
Muela	Butha-Buthe	intervention

Malefiloane	Mokhotlong	intervention
St. James	Mokhotlong	control
Moeketsane	Mokhotlong	control
Mapholaneng	Mokhotlong	intervention
Linakaneng	Mokhotlong	control
Molikaliko	Mokhotlong	intervention
Libibing	Mokhotlong	control
St Martins	Mokhotlong	intervention

Table 1. Clinic allocation.

3.3. Sample size

We calculated the sample size for the non-inferiority cluster randomized design which corresponds to an individually randomized design multiplied by a design effect (3–5). We will use odds ratios (ORs) to assess the effect of the intervention on our binary primary endpoint. An OR of 1 corresponds to no relative effect, an OR >1 to a positive relative and an OR <1 to a negative relative effect in the intervention versus control clusters. We aim at testing the null hypothesis H_0 : OR \leq margin of non-inferiority (NI) versus the alternative hypothesis H_1 : OR > NI, where the rejection of the null hypothesis implies non-inferiority. The NI margin for the OR of reaching our primary endpoint is set to 0.8 (see section 3.4).

We estimated an intraclass correlation coefficient of 0.04 as the proportion of the variance explained by the cluster structure in our population and included the estimated mean cluster size and standard deviation to our design effect. Our desired type I error rate was chosen as 0.025. With 9 clusters in the intervention group and 9 clusters in the control group, we will have 85% power to detect a one-sided difference of >10% in the primary endpoint between the intervention and the control arm.

3.4. Framework

This is a non-inferiority trial. If non-inferiority of the primary endpoint is established, we will assess superiority.

We chose a NI margin for the odds ratio of reaching our primary endpoint of 0.8, i.e., if the lower bound of the one-sided 97.5% confidence interval for the adjusted odds ratio for the primary outcome exceeds 0.8, then our intervention is non-inferior to standard of care. On an absolute scale, this non-inferiority margin corresponds to a higher absolute probability of failing to reach the primary endpoint of 5% in the intervention compared to the control group, if 65% of participants in the control arm will be engaged in care with documented viral suppression at 24 months follow-up.

If the lower bound of the two-sided 95% confidence interval for the adjusted odds ratio for the primary endpoint exceeds 1.0, we will consider our intervention superior.

3.5. Statistical interim analyses and stopping guidance

No interim analyses are planned.

3.6. Timing of final analysis

All outcomes will be analysed collectively after the trial was closed, this SAP signed, and the data freezed.

3.7. Timing of outcomes assessment

Table 2 shows the nominal visit months, the permitted ranges according to the protocol, and the ranges that will be used for analysis.

Nominal visit month	Window according to the protocol in months	Range used for analysis
12	4-16 months	- Months will be analysed as calendar months, i.e., for a participant enrolled on 10.10.2020 the 24 months window will be 10.02.2022 -10.02.2023.
24	16-28 months	If multiple viral loads are available in the outcome window, the closest measurement to the nominal visit month will be considered for analysis.

Table 2. Nominal visits and permitted windows.

4. Statistical principles

4.1. Confidence intervals and p-values

Statistical tests and 97.5% confidence intervals for non-inferiority comparisons will be one sided-sided. Statistical tests and 95% confidence intervals for superiority and equivalence comparisons will be two-sided. P-values will be presented where appropriate.

For the primary endpoint (non-inferiority and subsequently superiority testing) no statistical multiplicity adjustment will be needed because of the closed testing principle (6,7). If in the primary endpoint the intervention fulfills the non-inferiority criterion, secondary endpoints which may become the basis for additional claims will be evaluated hierarchically (8). Statistically significant effects in these secondary endpoints, which are part of our confirmatory strategy, could be considered for additional claims. Clinically relevant secondary endpoints are listed separately and will be evaluated independently of the result of the primary endpoint. They would require further investigation if significant differences were observed, but the primary objective has not been achieved. For the secondary endpoints expressing supportive evidence, no claims are intended, and only descriptive statistics will be presented.

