- We added a sensitivity analysis for the primary endpoint using imputation for VLs missing at 24 months in the ITT population.
- We added a sensitivity analysis for the primary endpoint in a per-protocol population including participants for whom all viral loads were available in the VITALapp ≤31 days after phlebotomy.

Primary endpoint	Population	Comparison
Proportion of participants engaged in care	ITT	i. Non-inferiority
(defined as documented visit attendance) with documented viral suppression (< 50 copies/mL) 24 months (16-28 months) after enrollment*		ii. Superiority

Sensitivity analysis for the primary endpoint

1.	Proportion of participants engaged in care	ITT	13.:
	(defined as documented visit attendance)		i. Non-inferiority
	with documented viral suppression (<1000 copies/mL) 24 months (16-28 months) after enrollment		ii. Superiority

 Proportion of participants engaged in care (defined as documented visit attendance) with documented viral suppression (<50 copies/mL) 24 months (16-28 months) after enrollment ITT using imputation for VLs missing at 24 months

PP*

 Proportion of participants engaged in care (defined as documented visit attendance) with documented viral suppression (<50 copies/mL) 24 months (16-28 months) after enrollment

4.	Proportion of participants with viral re-	ITT	45. hierarchical (i.e. 4.
	suppression (< 50 copies/mL) 24 months (16-		only if the primary
	28 months) after enrollment among all		endpoint is non-inferior,
	participants with an unsuppressed VL (≥ 50		and 5. only if 4 is
	copies/mL) during the first 12 months of		superior):
	follow-up		Superiority
	•		, ,
5.	Proportion of participants with sustained	ITT	
	viral suppression (defined as >1 VL <50		
	copies/mL) during 24 months follow-up		
	ondary endpoints indicative of clinical		
ber 6.	nefit or harm Rate of mortality at 12 and 24 months after	ITT	67.: Equivalence
٠.	enrollment		8.: Superiority
			on superiority
7.	Proportion of participants with confirmed TB		
	diagnosis at 12 and 24 months after		
	enrollment		
8.	Disengagement from care at 12 and 24		
	months after enrollment		
	ondary endpoints expressing supportive		
	dence Time to follow-up VL in case of an	ITT	913.: Superiority (for 9
9.	unsuppressed VL (≥ 50 copies/mL)	111	11. the upper bound of
	unsuppressed vi (2 30 copies/inii)		the 95% CI must be below
10	Time to ART regimen adaption in case of		1, and for 1213. the
10.	virologic failure**		lower bound of the 95% C

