Primary outcome: For the analysis of the primary outcome, we will use a multi-level logistic regression model including clinic cluster as a random effect, arm allocation and the randomization stratification factor (district) as a fixed effect. Unavailability of a viral load or only an invalid viral load result in the predefined primary endpoint window (for any reason) will be considered as failure. Results will be reported as adjusted odds ratios and absolute differences with confidence intervals. For the primary endpoint, non-inferiority in the ITT population and superiority in ITT will be assessed but no statistical multiplicity adjustment will be needed because of the closed testing principle. For the non-inferiority comparison, a confidence interval approach will be used. Under the assumptions of the sample size calculation, non-inferiority is compatible with the lower bound of the one-sided 97.5% confidence interval for the adjusted odds ratio for the primary outcome exceeding 0.8. A figure illustrating the confidence interval and the non-inferiority margin will be presented. If the non-inferiority is established, then we will assess for superiority by assessing whether the two-sided 95% confidence interval of the adjusted odds ratio excludes 1.

Assessment of cost (primary outcome): We will analyse cost-effectiveness if the intervention is found to be superior or assess the budget impact if the intervention is found to be non-inferior. For the cost-effectiveness analysis, we will use the primary endpoint and mathematical models of HIV transmission. Costing data will include: (1) conversion rate of local currency to U.S. dollars at 6-month intervals over the life of the project; (2) costs of all commodities used in the intervention; (3) average time clients spent with intervention including transportation, (4) staff time and representative salaries; (5) local average wages of the target population; (6) remunerations to clinics; and (7) other relevant costs, including training of providers and transport costs.

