Effect modification (primary outcome): For effect modification of the primary outcome the following variables will be considered:

- i. Age groups (18-24, 25-39, 40-59, and ≥60 years)
- ii. Gender (female, male)
- iii. Cell phone access (yes, no)

Analyses will be performed as for the main primary outcome analysis including an interaction term between these potential effect modifiers and the randomized group. If an interaction term is found to be significant (p-value<0.05), effect estimates will be summarized descriptively by subgroup categories. As the study is not powered for these pre-planned subgroup analyses, no formal hypothesis testing will be done.

Secondary endpoints which may become the basis for additional claims: In case non-inferiority of the primary endpoint is established, these will be evaluated hierarchically.

- 4. Proportion of participants with viral re-suppression (<50 copies/mL) 24 months (16-28 months) after enrollment among all participants with an unsuppressed VL (≥ 50 copies/mL) during the first 12 months of follow-up: This analysis will include individuals with a VL ≥50 copies/mL in the first 12 study months and then directly follow the primary endpoint analysis.
- 5. Proportion of participants with sustained viral suppression (defined as >1 VL <50 copies/mL) during 24 months follow-up: This analysis will directly follow the primary endpoint analysis with endpoint adapted to sustained viral suppression <50 copies/mL throughout the study. Sustained viral suppression is defined as >1 VL <50 copies/mL from study start to end of 24-month window (0-28 months) along with no VL ≥50 copies/mL.

Secondary endpoints indicative of clinical benefit or harm: These will be evaluated independently of the primary objective and without hierarchy / multiplicity adjustment.

- 6. **Rate of mortality at 12 and 24 months after enrollment:** This analysis will use Cox regression adjusted for clinic and district by study arm.
- 7. **Proportion of participants with confirmed TB diagnosis at 12 and 24 months after enrollment:** This analysis will directly follow the primary endpoint analysis with endpoint TB diagnosis (window: 0 months to primary endpoint or 28 months).
- 8. **Disengagement from care at 12 and 24 months after enrollment:** This analysis will directly follow the primary endpoint analysis with endpoint disengagement from care at 24 months, defined as neither a documented visit attendance nor a VL measurement (window: 16-28 months).

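### Primary superiority and endpoints 4 then 5 are both opened by non-inferiority at the full level, so the error rate across confirmatory superiority claims is uncontrolled

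*SAP*

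**What the plan says.** Primary non-inferiority is the entry condition for two sets of superiority tests.

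- **Branch A, primary superiority.** SAP section 3.4: "If non-inferiority of the primary endpoint is established, we will assess superiority". The criterion there is that the "lower bound of the two-sided 95% confidence interval for the adjusted odds ratio for the primary endpoint exceeds 1.0".
- **Branch B, endpoints 4 and 5.** SAP section 4.1, on the primary endpoint meeting the non-inferiority criterion: "secondary endpoints which may become the basis for additional claims will be evaluated hierarchically". SAP section 6.2: "In case non-inferiority of the primary endpoint is established, these will be evaluated hierarchically". Table 3 (section 6.1) allows endpoint 4 if the primary is non-inferior, "and 5. only if 4 is" superior.

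Section 4.1 makes superiority tests two-sided with 95% intervals. It describes endpoints 4 and 5 as belonging to the confirmatory strategy and as a possible source of further claims. On multiplicity, sections 4.1 and 6.2 give one argument, confined to the two hypotheses on the primary endpoint: "no statistical multiplicity adjustment will be needed because of the closed testing principle".

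The 2.5% level appears in section 3.3: "Our desired type I error rate was chosen as 0.025". It stands there next to the non-inferiority test on the primary endpoint. No section sets a rate for the whole set of claims.

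**The concern.** Each branch is ordered internally: non-inferiority then superiority in A, and endpoint 4 then 5 in B. Nothing orders A against B. If primary superiority is not shown, endpoint 4 is still tested at the full level. If endpoint 4 fails, primary superiority may still be claimed. A hierarchy controls error across claims only if the claims form a single sequence or share the level, and here they do neither.

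Both branches lead to claims. Superiority on the primary is a named secondary objective (section 2.2) and decides whether a cost-effectiveness analysis follows (section 6.2). Endpoints 4 and 5 are singled out in section 4.1 as claimable. At stake is the chance that the trial reports some superiority finding as confirmed when neither the primary endpoint nor endpoint 4 differs between arms.

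**Working it through.** **Inputs from the SAP.** Per-test level 0.025 (3.3); margin, "The NI margin for the OR of reaching our primary endpoint is set to 0.8"; 9 clusters per arm and intraclass correlation 0.04 (3.3); control proportion 65% (3.4).

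**Assumed.** True primary odds ratio 1; no effect on endpoint 4; test statistics bivariate normal with correlation ρ. Endpoint 4 uses a subset of the same participants and the same 24-month window, so a positive ρ is plausible, but its value is unknown. Section 3.3 does not give the mean and spread of cluster size, so the standard error is bounded rather than computed.

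**1. The plan's own figures.** A one-sided 97.5% bound, or the lower bound of a two-sided 95% interval, gives 0.025 per test, which agrees with 3.3. For the margin, the odds at 65% are 0.65/0.35 = 1.857; × 0.8 = 1.486, a proportion of 0.598. The gap is 5.2 points, consistent with the 5% in 3.4.

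**2. Smallest standard error.** With equal clusters of size m, the effective size per arm is 9m / (1 + (m − 1) × 0.04). This tends to 9/0.04 = 225 as m grows without limit. Then SE(log OR) = √(2 / (225 × 0.65 × 0.35)) = √(2/51.19) = 0.198. At m = 200 the effective size is 200.9 and the SE is 0.209. Unequal clusters raise it further. So about 0.20 is a floor.

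**3. Chance of reaching branch B.** Let Z1 and Z2 be the statistics for primary superiority and endpoint 4. Non-inferiority is met when Z1 > c, with c = ln(0.8)/SE + 1.96. At SE 0.20, c = −0.223/0.20 + 1.96 = 0.844, and P(Z1 > 0.844) = 0.199.

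**4. Chance of at least one false superiority claim.**

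P(Z1 > 1.96) + P(Z1 > c, Z2 > 1.96) − P(Z1 > 1.96, Z2 > 1.96)

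At SE 0.20 and ρ = 0: 0.025 + 0.199 × 0.025 − 0.025² = 0.025 + 0.0050 − 0.0006 = 0.0294.

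| SE | ρ = 0 | 0.3 | 0.5 | 0.7 |
|---|---|---|---|---|
| 0.20 | 2.9% | 3.4% | 3.6% | 3.8% |
| 0.10 | 4.0% | 4.4% | 4.4% | 4.2% |
| 0.05 | 4.9% | 4.8% | 4.5% | 4.2% |

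At SE 0.20 and ρ = 0.9 the figure is 3.5%. The Bonferroni bound is 0.025 + 0.025 = 5%.

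**5. What the lower rows require.** SE 0.10 needs an effective size of 2 / (0.01 × 0.2275) = 879 per arm. Even with unlimited cluster size, that means an intraclass correlation of 9/879 = 0.010, a quarter of the planned 0.04. SE 0.05 needs 9/3516 = 0.0026.

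**6. Endpoint 5.** When all null hypotheses hold it adds nothing, because it is reached only after endpoint 4 has already been falsely rejected.

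**7. After repair.** In one fixed sequence, with neither endpoint different, any false superiority claim must begin with primary superiority, so the rate is 2.5% whatever ρ and SE. With 0.0125 for each branch the rate is at most 2.5%: 1 − 0.9875² = 2.48% if the tests are independent and non-inferiority is always met.

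**The case against.** The strongest defence is that the structure is deliberate and consistent. Non-inferiority is the primary objective (section 2.2), and opening secondary claims once that objective is met is a recognisable strategy for a non-inferiority trial. Sections 4.1 and 6.2 and Table 3 agree on the order. This stands: there is no internal contradiction, and requiring primary superiority before endpoint 4 is a different strategy, not the correction of a slip. It does not answer the point that the chosen strategy leaves the claims without joint error control while calling them confirmatory.

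Three stronger readings are tempting, and the SAP does not support them.

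- *The plan breaches its own family-wise level.* It states none. The 0.025 in section 3.3 belongs to the primary test; 2.5% is the benchmark here because it is the favourable-direction level of each test.
- *The closed-testing statement is wrong.* It is limited to the primary endpoint, and for that it is right.
- *The error rate is close to 5%.* Under the planned intraclass correlation, cluster number and control rate it is not. Non-inferiority is reached only about 20% of the time at a true odds ratio of 1, which limits the excess.

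The calculation also takes the least favourable case for branch A. If the primary odds ratio is truly above 1, primary superiority is no longer a false claim. If it is below 1, both the false superiority rate and the chance of reaching endpoint 4 fall.

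**Conclusion.** The point holds in a limited form. Two unlinked superiority branches each run at 2.5% in the favourable direction after non-inferiority, and the only multiplicity argument offered covers one of them. Under the assumptions above, the chance of at least one false superiority claim is about 2.9% to 3.8% at the planned floor for the standard error, an excess of roughly 0.4 to 1.3 percentage points over 2.5%. A larger SE within the planned inputs makes the excess slightly smaller at the same correlation. Figures of 4% and above need an achieved intraclass correlation of about 0.01 or less.

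A reader might infer that the main result is compromised. It is not: non-inferiority followed by superiority on the primary endpoint, taken alone, stays at 2.5%. What is affected is the confirmatory standing of superiority claims taken together, in particular a claim on endpoint 4 or 5 made without primary superiority. This should be put right, but it does not threaten the trial's primary conclusion.

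**What to change.** In section 4.1, Table 3 and section 6.2, state one fixed sequence: primary non-inferiority, primary superiority, endpoint 4, endpoint 5, each tested only if the one before it is met.

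If endpoint 4 must be claimable without primary superiority, choose one of these:

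- A fixed split after non-inferiority: 0.0125 one-sided for primary superiority and 0.0125 for the chain 4 then 5. The price is power: a test with 85% power at 0.025 keeps about 77% at 0.0125.
- An explicit alpha-passing rule that includes endpoint 5. A plain Holm step between primary superiority and endpoint 4 is not enough. If endpoint 4 truly works and is rejected, Holm raises primary superiority to 0.025; testing endpoint 5 at 0.0125 as well gives 1 − 0.975 × 0.9875 = 3.7% when those two are null, the tests are independent and non-inferiority is met.
- Keep the present scheme, say that error control covers the primary endpoint only, and label endpoints 4 and 5 non-confirmatory.

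No new data are needed. With the fixed sequence or the split, endpoints 4 and 5 can be claimed less often. Section 1.4 records that version 1.1 was revised during analysis, so a further change must be dated, justified and disclosed. The fixed sequence only adds a condition for a claim on endpoints 4 and 5, so it cannot favour the intervention.

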	virologic failure		must be above 1)
11.	Rate of clinic visits at 24 months after		must be above 1,
	enrollment		
12.	Proportion of participants with ART regimen		
	modification due to virologic failure at 12		
	and 24 months among participants with		
	virologic failure**		
12	Proportion of participants having ever		
	opo. don or participants naving ever		

Table 3. Primary and secondary endpoints as well as sensitivity analyses. *The per-protocol analysis includes participants for whom all viral loads were available in the VITALapp ≤31 days after phlebotomy. **Virologic failure is defined according to the implementation in VITAL, i.e. two consecutive VLs ≥1'000 copies/mL or three consecutive VLs ≥20 copies/mL from VITAL start - 22.12.2022 and two consecutive VLs ≥50 copies/mL from 23.12.2022 – VITAL closure.

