Secondary endpoints expressing supportive evidence:

- 9. Time to follow-up VL in case of an unsuppressed VL (≥ 50 copies/mL): This analysis will consider the time in weeks to follow-up VL in case of an unsuppressed VL (≥ 50 copies/mL) as outcome and use a multi-level linear regression model including clinic cluster as a random effect, arm allocation and the randomization stratification factor (district) as a fixed effect.
- 10. Time to ART regimen adaption in case of virologic failure: This analysis will consider the time in weeks to ART regimen adaption in case of virologic failure (defined as two consecutive VLs ≥1'000 copies/mL or three consecutive VLs ≥20 copies/mL from VITAL start 22.12.2022 and two consecutive VLs ≥50 copies/mL from 23.12.2022 − VITAL closure) as outcome and use a multi-level linear regression model including clinic cluster as a random effect, arm allocation and the randomization stratification factor (district) as a fixed effect.
- 11. Rate of clinic visits at 24 months after enrollment: This analysis will consider the number of clinic visits throughout the study period as outcome and use and use a multi-level Poisson regression model with offset study duration including clinic cluster as a random effect, arm allocation and the randomization stratification factor (district) as a fixed effect.
- 12. Proportion of participants with ART regimen modification due to virologic failure at 12 and 24 months among participants with virologic failure: This analysis will only include people with a virologic failure (defined as two consecutive VLs ≥1′000 copies/mL or three consecutive VLs ≥20 copies/mL from VITAL start 22.12.2022 and two consecutive VLs ≥50 copies/mL from 23.12.2022 VITAL closure). Then, this analysis will directly follow the primary endpoint analysis with endpoint ART modification.
- 13. **Proportion of participants having ever received TPT:** This analysis will directly follow the primary endpoint analysis with endpoint having ever received TPT by 24 months.

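### Table 3 gives supportive endpoints 9–13 a superiority rule that section 4.1 excludes, and the rule has the wrong null value for endpoints 9–10 as modelled

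*SAP*

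**What the plan says.** Three parts of the SAP deal with endpoints 9 to 13, the supportive-evidence group.

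- **Section 4.1** sets their status: "For the secondary endpoints expressing supportive evidence, no claims are intended, and only descriptive statistics will be presented". It also fixes the level for any superiority comparison: "Statistical tests and 95% confidence intervals for superiority and equivalence comparisons will be two-sided".
- **Table 3 (section 6.1)** lists the five endpoints under the supportive-evidence heading and enters superiority as the comparison. For 9–11 the upper limit of "the 95% CI must be below" 1. For 12–13 the lower limit "must be above 1". Endpoints 4 and 5 carry an explicit gate in the same table; 9–13 carry none.
- **Section 6.2** gives each endpoint a model with an arm term. For 9 and 10, times in weeks, the plan is to "use a multi-level linear regression model including clinic cluster as a random effect, arm allocation" and district. Endpoint 11 gets a "multi-level Poisson regression model with offset study duration". Endpoints 12 and 13 follow the primary analysis, a mixed logistic model reported as an adjusted odds ratio. No threshold or verdict is stated there for any of the five.

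The SAP does not say which section prevails. Its revision table (section 1.4) dates the changes in version 1.1 to the analysis period.

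**The concern.** A superiority comparison with a confidence-limit criterion is a hypothesis test, and a model-based odds ratio or rate ratio is more than a descriptive statistic. Section 6.2 itself separates outcome summaries (medians, quartiles, counts, percentages) from regression estimates. An analyst following 4.1 would report summaries by arm and stop. An analyst following Table 3 would report a superiority result on time to follow-up viral load, time to regimen change, clinic visits, regimen modification or TPT.

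At stake is what the report may say about these five endpoints. Because the SAP was last revised during analysis, the choice between the two readings could be made with results in view unless the text is settled and the change dated.

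**Working it through.** **1. The sections side by side.**

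| Endpoints | 4.1 | Table 3 | 6.2 model | Null value of the arm effect |
|---|---|---|---|---|
| 9, 10 | descriptive, no claim | superiority, upper limit < 1 | linear, weeks | 0 (difference) |
| 11 | descriptive, no claim | superiority, upper limit < 1 | Poisson | 1 (rate ratio) |
| 12, 13 | descriptive, no claim | superiority, lower limit > 1 | logistic | 1 (odds ratio) |

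The second and third columns conflict in every row. In the first row the Table 3 threshold also does not match the null value of the model.

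**2. Error rate if Table 3 is followed.** The SAP gives no family-wise figure for these endpoints, so there is none to reproduce. A two-sided 95% interval puts 0.05 / 2 = 0.025 in the favourable direction. With no true effect on any endpoint, independent tests and the correct null value in each:

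- five tests: 1 − 0.975^5 = 0.119, or 11.9%;
- upper bound under any dependence: 5 × 0.025 = 12.5%;
- six tests, if endpoint 12 is judged at both 12 and 24 months: 1 − 0.975^6 = 0.141, or 14.1%.

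**3. The rule for endpoints 9 and 10.** Let d be the estimated difference in weeks, intervention minus control, with standard error SE. The rule passes when d + 1.96 × SE < 1. If the true difference is 0, the pass probability is Φ(1/SE − 1.96). The SAP gives no SE, so a range is assumed:

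- SE 1 week: Φ(−0.96) = 16.9%;
- SE 2 weeks: Φ(−1.46) = 7.2%;
- SE 4 weeks: Φ(−1.71) = 4.4%.

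The intended rate is 2.5%. In weeks, an upper limit below 1 excludes only a delay of a week or more. That is a non-inferiority statement with a one-week margin, not superiority.

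**4. Both together.** With two endpoints at the rates in step 3 and three at 2.5%, all independent, the chance of at least one false pass is 1 − (1 − p)^2 × 0.975^3:

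- p = 0.1685: 1 − 0.8315^2 × 0.9269 = 35.9%;
- p = 0.0721: 1 − 0.9279^2 × 0.9269 = 20.2%;
- p = 0.0436: 1 − 0.9564^2 × 0.9269 = 15.2%.

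The 11.9% therefore holds only if times are analysed on a scale that gives a ratio.

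**The case against.** The strongest reply is that the harm is already barred. Section 4.1 rules out claims on these endpoints and nothing later withdraws that. Table 3 keeps the supportive label, and a stated direction of benefit can sit beside a no-claims rule. On this view only the restriction to descriptive statistics is loosely worded. Much of this stands, and it limits the point to an inconsistency within a no-claims tier. It does not remove it: Table 3 uses the language of a requirement, and the SAP gives no order of precedence.

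A reader might infer that these verdicts could rescue the intervention after a failed primary, or that they inflate the trial's confirmatory error. The document does not support this. The primary endpoint and endpoints 4–5 have their own hierarchy, which 9–13 do not enter, and 4.1 forbids claims on 9–13 whatever the primary shows. Nor is the absence of a multiplicity adjustment a separate fault: it is consistent with a tier from which nothing is to be claimed.

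The figures also have limits that stand. No effect on all five endpoints is a hard assumption for endpoint 11, since fewer visits are part of the rationale for the care model (section 2.1). Leaving it out gives 1 − 0.975^4 = 9.6%. The count of five is nominal, because section 6.2 fits no model when events per parameter are too few. Section 6.2 also lets continuous variables be transformed. A log scale for time would give a ratio with null value 1, and the Table 3 rule would then be correct for 9 and 10. But the entries for those endpoints name time in weeks and no transformation.

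**Conclusion.** The SAP is inconsistent as written: section 4.1 and Table 3 cannot both be applied to endpoints 9–13. It might be read as though section 6.2 also prescribes a superiority test, but it supplies models only; the pass rule is in Table 3 alone.

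The consequence is confined to what may be reported on five supportive endpoints. If Table 3 governed, the chance of at least one false superiority result would be about 11.9%, given no true effects, independence and correct null values, and at most 12.5% without independence. If 4.1 governed, there would be no test and no such error. Separately, the Table 3 rule is wrong for endpoints 9 and 10 on an untransformed weeks scale. How far wrong depends on a standard error the SAP does not give. The point should be corrected but does not threaten the primary conclusion.

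**What to change.** - **Table 3, endpoints 9–13:** replace the superiority entry and the confidence-limit rule with *estimate with two-sided 95% CI; no superiority conclusion*. This also removes the wrong threshold for 9 and 10.
- **Section 4.1:** replace the restriction to descriptive statistics with *estimates with 95% CIs, no hypothesis test and no claim*.
- **Section 6.2:** keep the models, as estimation only.
- **Section 1.4:** record the change and when it was made relative to the analysis.

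An alternative is to amend 4.1 to permit unadjusted exploratory tests. The text would then agree, but the null value for 9 and 10 would have to be corrected in Table 3, or a ratio scale fixed in 6.2.

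The cost is a few lines of SAP text and a dated revision entry. No estimate is lost; the price is that no superiority label can be attached to endpoints 9–13.
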